This is an open label, investigator-sponsored, pilot study. Subjects agreeing to participate in the study and meeting the eligibility criteria assessed at the screening visit will be enrolled in the study. The length of time between screening and treatment will last between 0 days to a maximum of 12 weeks. Subjects who enter the screening phase during a cluster headache episode and meet the study eligibility criteria can immediately enter the treatment phase and may opt to treat their cluster headache episode in the clinic. Subjects who are not in a cluster headache episode, who meet initial screening eligibility criteria, can remain in the screening phase for up to 12 weeks until their next cluster episode begins. Upon initiation of a cluster headache episode, subjects will enter the treatment period. Subjects will be trained on the proper use of the hand-held dispenser containing CO₂ calibrated to deliver 0.5 standard liters per minute (SLPM). This dispenser will be provided for use in the clinic or home. Subjects will be instructed to use the nasal CO₂ dispenser, 10 seconds/nostril, as needed up to 6 times to treat one attack. Each dose must be separated by 3-5 minutes. Subjects should treat only one attack in a 24-hour period. Subjects may treat up to three cluster headache attacks during the treatment phase of this study. One hour after the first dose, subjects can choose to treat with investigator-approved rescue medication. Subjects will be asked to complete an online diary after the completion of the dosing. Diary assessments will collect pain severity (0=none, 1=mild, 2=moderate, 3=severe), symptoms (such as tearing, nasal congestion, and running nose), nasal CO₂ usage, acute medication usage, satisfaction of treatment, number of cluster attacks, and unusual symptoms. Subjects will be contacted by phone within 3 days of the first use of the nasal CO₂ dispenser to assess adverse events (AEs) and medication usage. A total of 25 subjects will enter the treatment period and be instructed to treat up to 3 cluster headaches with nasal CO₂. Within 7 days of treating their last cluster headache episode, subjects will return for an end of study visit.

Number of Subjects:	Up to 25 subjects enrolled and treating up to 3 cluster headaches in one cluster headache period.

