13. Recurrent nose bleeds, which in the opinion of the Investigator, may interfere with the study.
14. Is participating in any other therapeutic clinical investigation or has participated in a clinical trial and received treatment in the preceding 30 days.

Investigational Product:	0.17 L CO ₂ delivered through two 10 second administrations in each nostril, up to 6 times, to treat one attack (total of 1.0 L CO ₂). Subjects may treat up to three cluster headache attacks during the treatment phase of this study (total of 3.0 L CO ₂).
Efficacy Evaluation:	Primary Endpoints: Greatest change from pre-treatment headache pain intensity to post treatment at any time point within 30 minutes of Nasal CO ₂ administration.
	Secondary Endpoints: 
• Percentage of subjects experiencing headache pain freedom at 5-60 minutes within the treated attack• Percentage of subjects with headache relief at 5-60 minutes within the treated attack• Rescue medication usage for treated attack• Subject satisfaction• Cluster recurrence
Safety Evaluation:	Safety assessments will include: 
• Monitoring adverse events (AEs)• Concomitant medications
Statistical Methods:	Descriptive statistics will establish baseline characteristics and adverse event frequency. Data for each of the primary and secondary outcome measures will be statistically analyzed for within group changes via a 2-tailed repeated measures ANOVA and or independent or dependent t-tests as appropriate. All ANOVAs will be followed by univariate post-hoc tests.

Protocol 15-001CA
Nasal CO₂

Schedule of Events:

Study Procedures	Screening	Treatment	End of Study Visit¹
Informed Consent	X		
Eligibility	X		
Medical History/ Medications / Demographics	X		
Physical Examination with Neurological and Nasal Mucosal Exam	X		X
Vital Signs	X		X
Urine Pregnancy Test	X		X
Subject Training	X		
Subject eDiary, AE/ConMed diary, and Questionnaire Instruction	X		
Investigational Product Dispensation	X	X ²	
Accountability of Investigational Product and Study Supplies	X		X
Diary Completion		X	
Adverse Event Assessment		X	X
Concomitant Medications Assessment	X	X	X
Telephone Contact		X ³	X
eSource Document and eCRF Completion	X		X

¹ The End of Study Visit should occur within 7 days after the subject treats up to his/her third headache or within 7 days after the completion of the 84-day treatment period, whichever occurs first.

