5.2 Study Treatment

5.2.1 Dose Description

This is an open-label study so all eligible subjects will receive a nasal CO₂ hand-held dispenser. One dose will consist of a 10 second administration of nasal CO₂ to each nostril. Subjects will be instructed to use the nasal CO₂ dispenser, 10 sec/nostril, as needed up to 6 times to treat one attack. Each dose must be separated by 3-5 minutes. Subjects should treat only one attack during a 24-hour period with the investigational product. Subjects may treat up to three cluster headache attacks during the treatment phase of this study.

Subjects may receive up to a total of 1.0 L of CO₂ if they treat one attack with 6 doses. Subjects may receive a total of 3.0 L of CO₂ if they treat three headache attacks with 6 doses of CO₂ during this study.

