10.0 STATISTICAL METHODS AND ANALYSIS

10.1 General Considerations

Tests will be conducted with a two-sided alpha = 0.05. Descriptive statistics and 95% confidence intervals will be presented with all analyses.

One interim analyses will be performed after 12 subjects have completed the study. All efficacy and safety analyses will be performed at the conclusion of the study.

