10.3.3 Secondary Efficacy Endpoints

The key secondary endpoints are:

Protocol 15-001CA
Nasal CO₂

- Percentage of subjects experiencing headache pain freedom at 5-60 minutes within the treated attack
- Percentage of subjects with headache relief at 5-60 minutes within the treated attack
- Rescue medication usage
- Subject satisfaction
- Cluster recurrence

This analysis will be assessed for the first headache treated with the investigational product.

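### The only tests named for the secondary endpoints are t-tests and repeated-measures ANOVA of within-group change, which do not suit percentages or outcomes that exist only after treatment

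*Combined protocol and SAP*

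**What the plan says.** The only sentence that names a test is in the synopsis, under Statistical Methods. Primary and secondary outcome data are to be "statistically analyzed for within group changes via a 2-tailed repeated measures ANOVA and or independent or dependent t-tests as appropriate", and "All ANOVAs will be followed by univariate post-hoc tests". Section 10.1 adds "Tests will be conducted with a two-sided alpha = 0.05" and, as a separate sentence, "Descriptive statistics and 95% confidence intervals will be presented with all analyses". It does not say how the intervals are computed.

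Sections 10.5 to 10.7 give the population, the attacks analysed and the multiplicity position, but no test or interval method. Section 10.11 treats Sections 10.1 to 10.11 as the statistical analysis plan, and no further document is promised.

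Section 10.3.3 lists five key secondary endpoints. The first is "Percentage of subjects experiencing headache pain freedom at 5-60 minutes within the treated attack"; the others are the percentage with headache relief over the same window, rescue medication use, subject satisfaction and cluster recurrence. Section 10.6 analyses them for the first treated attack and for all treated attacks.

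There is one arm: "This is an open-label study so all eligible subjects will receive a nasal" CO₂ dispenser (Section 5.2.1). Section 10.7 mentions two treatment groups when it describes exposure, but the design has no second group.

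**The concern.** A test of within-group change needs a value before treatment and one after, on a scale where a mean difference is meaningful. None of the five key secondary endpoints clearly meets that description. The qualifier that lets the analyst choose as appropriate selects among the listed methods, and none of those is a method for a proportion.

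In an uncontrolled pilot, the response rate and its interval are the main product of the secondary analysis. They will also be looked at early. Section 10.3.2 runs all efficacy analyses once 12 subjects have treated at least one attack, and Section 10.9 allows early termination for efficacy or lack of it, although it ties no decision to these endpoints. If the choice of method is left until the data are visible, a small count could be reported as a significant change, or as a rate of zero with no uncertainty.

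**Working it through.** **Inputs.** Maximum n is 25 (synopsis: "Up to 25 subjects enrolled and treating up to 3 cluster headaches in one cluster headache period"). The early look has n = 12 (Section 10.1: "One interim analyses will be performed after 12 subjects have completed the study"). The analysed number may be lower, because efficacy uses the mITT set (Section 10.4.2). Assessments are at 5, 15, 30 and 60 minutes (Section 8.1.9). The documents give no expected response rate for cluster headache, so true rates of 5% to 50% are assumed. They also contain no power or interval calculation to reproduce.

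**Step 1: each endpoint against the named methods.**
- Pain freedom: 0/1 per subject. If a treated attack starts with pain, the pre-dose value is 0 for everyone.
- Headache relief: 0/1 per subject; relief is not defined.
- Rescue use: allowed only after the one-hour assessment (Section 7.2.3), so there is no pre-treatment value.
- Satisfaction: exists only after treatment; no scale is given.
- Recurrence: exists only after treatment; not defined.
- Independent t-test: no second treatment group, and no other grouping is named.

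**Step 2: dependent t-test of pain freedom.** With x responders of n and a pre-dose value of 0, let p = x/n. Then t = p / √(p(1−p)/(n−1)) on n−1 degrees of freedom. The exact McNemar p-value is 2 × 0.5^x. For 4/25, t = 0.16 / √(0.16 × 0.84 / 24) = 2.14.

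| Responders | t-test p, n=25 | t-test p, n=12 | Exact McNemar p |
|---|---|---|---|
| 3 | 0.083 | 0.082 | 0.25 |
| 4 | 0.043 | 0.039 | 0.125 |
| 5 | 0.022 | 0.017 | 0.0625 |
| 6 | 0.011 | 0.007 | 0.031 |

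The two tests disagree at the 0.05 level only at 4 and 5 responders. The null hypothesis in both is that nobody becomes pain free. With n=25 and a true rate of 20%, the chance of at least 4 responders, and so of a significant t-test, is 77%.

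**Step 3: a t-based interval, if that were the choice.** The interval is p ± t(0.975, n−1) × √(p(1−p)/(n−1)), set beside the exact (Clopper-Pearson) interval.

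| Result | t-based 95% | Exact 95% |
|---|---|---|
| 0/12 | 0 to 0% | 0 to 26.5% |
| 0/25 | 0 to 0% | 0 to 13.7% |
| 1/25 | −4.3 to 12.3% | 0.1 to 20.4% |
| 3/25 | −1.7 to 25.7% | 2.5 to 31.2% |
| 5/25 | 3.1 to 36.9% | 6.8 to 40.7% |
| 12/25 | 27.0 to 69.0% | 27.8 to 68.7% |

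For zero responders the exact upper limit is 1 − 0.025^(1/n), which is 0.265 at n=12 and 0.137 at n=25.

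**Step 4: true coverage of the nominal 95% t-based interval.** Add the binomial probabilities of every x whose interval contains the true rate. At 5% and n=25 the interval misses at x=0 (0.95^25 = 0.2774) and at x of 6 or more (0.0012), so coverage is 1 − 0.2774 − 0.0012 = 0.721. At 5% and n=12 it misses at x=0 (0.5404) and at x of 5 or more (0.0002), which leaves 0.459.

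| True rate | n=25 | n=12 |
|---|---|---|
| 5% | 0.721 | 0.459 |
| 10% | 0.926 | 0.717 |
| 20% | 0.896 | 0.927 |
| 36% | 0.962 | 0.956 |
| 50% | 0.957 | 0.961 |

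Over rates of 30% to 70%, coverage runs from 0.923 to 0.965 at n=25 and from 0.905 to 0.965 at n=12. The exact interval covers at least 95% by construction. Over rates of 5% to 50%, Wilson averages about 0.95 to 0.96, with minima of 0.914 (n=12) and 0.923 (n=25).

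**Step 5: repeated-measures ANOVA on the four 0/1 time points.** This was simulated with no time effect, an assumed correlation of 0.6 and 10,000 runs per setting. Type I error was 0.047 (n=25, rate 40%), 0.019 (n=25, rate 10%) and 0.004 (n=12, rate 10%), close to Cochran's Q (0.042, 0.016, 0.003). At a rate of 5% it could not be computed in 16% of runs (n=25) and 43% (n=12).

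**The case against.** The best defence is that the plan is loose rather than wrong, and much of that stands. No section prescribes a t-based interval, so an exact interval would comply with Section 10.1 as written. ANOVA across the post-dose time points did not inflate type I error in the simulation. Satisfaction could turn out to be a numeric score. The McNemar contrast affects only two counts, and its null is uninformative whichever test is used. The poor coverage is confined to low rates (and, by symmetry, very high ones). At the migraine pain-free rates quoted in the background (23%, 36%, 38.5%), which are reference points only, coverage at n=25 is 0.933, 0.962 and 0.935.

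A reader might go further and infer that every secondary interval and p-value at 25 or fewer subjects will be wrong or undefined. The documents do not support that: the interval method is open, and even a t-based one is adequate at middling rates. A reader might also take Section 10.1 to promise a test for every analysis. It attaches only descriptive statistics and intervals to all analyses; the synopsis sentence alone brings the secondary endpoints under a test. That sentence covers primary and secondary outcomes, not exploratory ones.

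What the defence does not supply is a method. The plan names tests for these endpoints and none of them estimates a response rate. Three endpoints have no change to test.

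**Conclusion.** The named tests do not suit the key secondary endpoints, and this should be corrected. The effect is limited: these are secondary endpoints, unadjusted for multiplicity, in an open-label pilot. Nothing here shows a problem with the primary endpoint, which is a change score, and no replacement test for it is argued.

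If the sentence is followed for pain freedom, 4 or 5 responders of 25 are declared significant where an exact test does not agree. If the unspecified intervals were t-based, coverage at an assumed true rate of 5% would be 72% with 25 subjects and 46% with 12, while at about 30 to 50% with 25 subjects it would be close to nominal. The size therefore depends on an unknown response rate. Low rates are plausible at the 5-minute assessment, but the documents do not give one. The t-test result also assumes that every treated attack has pain before dosing.

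**What to change.** Amend the Statistical Methods sentence in the synopsis and Section 10.6, before the 12-subject look:
- For the first treated attack, report count, percentage and a 95% interval for pain freedom and headache relief at each time point, and for any rescue use and any recurrence. Choose exact (Clopper-Pearson) or Wilson in advance. Run no within-group t-test on these endpoints.
- Define relief and recurrence so that each is a yes/no outcome per subject.
- Summarise satisfaction descriptively on its stated scale.
- For the all-headaches analysis, where a subject can contribute up to three attacks, use a method that accounts for attacks within subject, such as GEE or a subject-cluster interval. A simple binomial interval over attacks would treat them as independent.
- If time points are to be compared, name Cochran's Q or a repeated binary model.
- Delete the independent t-test, or name its groups.

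The cost is wording only, with no new data, visits or subjects. The downside is that exact intervals are wider when responders are few (at 1/25 the width is 20.3 points against 16.6 for the t-based interval), and some nominal p-values disappear.

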2.0 LIST OF ABBREVIATIONS

Abbreviation or Term	Definition/Explanation
AE	Adverse Event
AR	Allergic Rhinitis
°C	Degrees Celsius
CDDS	Carbon Dioxide Drug Delivery System
CFR	Code of Federal Regulations
CGRP	Calcitonin Gene-Related Peptide
CO ₂	Carbon Dioxide
CRF	Case Report Form
ECG	Electrocardiogram
EU	European Union
°F	Degrees Fahrenheit
FDA	Food and Drug Administration
GCP	Good Clinical Practice
H ⁺	Proton
H ₂ CO ₃	Carbonic Acid
HCO ₃ ⁻	Bicarbonate
ICH	International Conference on Harmonization
ICHD-II	International Classification of Headache Disorders-II
IHS	International Headache Society
IRB	Institutional Review Board
IVRS	Interactive Voice Response System
L	Liter
MedDRA®	Medical Dictionary for Regulatory Activities
Mg	Milligram
Min	Minute
mL	Milliliter
NSAIDS	Non-Steroidal Anti-Inflammatory Drugs

Protocol 15-001CA
Nasal CO₂

Abbreviation or Term	Definition/Explanation
NSAE	Non-Serious Adverse Event
PAR	Perennial Allergic Rhinitis
pCO ₂	Partial Pressure of Carbon Dioxide
PE	Physical Examination
pH	Log of the Hydrogen Ion Concentration
PP	Per Protocol Population
SAE	Serious Adverse Event
SAR	Seasonal Allergic Rhinitis
Sec	Second
SLPM	Standard Liters Per Minute, flow rate measured at a standard condition (25 °C and 1 bar)
TMD	Temporomandibular Disorder
TNSS	Total Nasal Symptom Score
TSA	Transportation Security Administration
US	United States
WHO-DRL	World Health Organization-Drug Reference List

3.0 BACKGROUND

3.1 Investigational Product

Capnia, Inc. is developing nasal, non-inhaled carbon dioxide (CO₂) for the symptomatic relief of diseases which may be mediated by the trigeminal nerve, including acute migraine and allergic rhinitis. Carbon dioxide, the active pharmaceutical ingredient, is CO₂ at $\geq 99.0\%$ volume.

Carbon dioxide is a naturally occurring gas that readily diffuses across body tissues and membranes. Although the exact mechanism of action(s) of CO₂ is unknown, in vitro studies with cultured neurons have shown that CO₂ reduces intracellular pH while simultaneously suppressing neuropeptide secretion, in particular calcitonin gene-related peptide (CGRP).¹ It is hypothesized that upon application to the nasal mucosa, CO₂ diffuses into local tissue and upon interaction with water, forms carbonic acid (H₂CO₃), which subsequently releases a proton (H⁺) and bicarbonate (HCO₃⁻). The locally-released protons cause a drop in local tissue pH, which leads to depolarization and subsequent inactivation of local neurons. The inactivation of neurons likely coincides with inhibition of the release from the trigeminal nerve of CGRP and other inflammatory mediators implicated in the pathogenesis of migraine and other trigeminally-mediated diseases.

3.2 Cluster Headache

Cluster headache is a seriously debilitating disorder with 14 million individuals worldwide currently seeking treatment.² Characterized by recurrent bouts of excruciating unilateral pain with accompanying ipsilateral autonomic symptoms such as lacrimation, conjunctival erythema, nasal congestion, rhinorrhea, and occasionally a partial Horner's syndrome.³ Cluster headaches typically last between 15-180 minutes with 75% of attacks lasting less than 60 minutes if left untreated.⁴ They occur at a frequency of several times per day to several times a week with a cluster period typically lasting 8-12 weeks.

Cluster headaches are classified separately from migraine on the basis of more severe pain, more frequent attacks, shorter duration of attacks, different autonomic symptoms, and a different underlying pathophysiology. Interestingly, while migraine headaches are more commonly diagnosed in women, cluster headaches are up to 3 times more prevalent in men.^{3,4} Currently, the etiology cause of cluster headaches is not fully understood, however, there has been an increased interest in the role of the sphenopalatine ganglion (SPG) and trigeminal ganglion in cluster headache.⁶ Both of these ganglion innervate the sinuses and offer a potential therapeutic target for the treatment of cluster headache. Current standard of care treatments included both abortive and prophylactic medications; both with limited efficacy. During the onset of headache, many people respond to high flow oxygen and triptans have been shown to reduce severity and duration of attack, although do not demonstrate long-term prophylactic effects.

The social and economic burden of cluster headache is significant. Patients with chronic and active episodic cluster headache are severely impacted in non-economic and economic of their lives. A study by D'Amico et al found a 36% of cluster headache patients have lost their jobs and half the patients have reduced work time by at least 50%.⁷

Considering the inadequacy of current pharmacological therapy at considerable economic and social burden of this debilitating disorder, further research is warranted on alternative treatment options.

3.3 Non-Clinical and Clinical Data

This section provides a brief summary of non-clinical and clinical data obtained to date. Additional Pharmacology/Toxicology as well as clinical safety information are summarized in the Investigator's Brochure. Toxicology studies have been conducted in rats as well as rabbits. Preliminary data is summarized in the Investigator's Brochure.

3.3.1 *In Vitro* Non-Clinical Evaluations

Experiments in primary cultures of rat trigeminal ganglia showed that CO₂ treatment of culture under isohydric conditions (i.e., buffered to prevent extracellular acidification), significantly suppressed the stimulatory effects of various stimuli on CGRP release.

These experiments provide evidence of a potentially unique mechanism of action by which CO₂ inhibits sensory nerve activation and subsequent release of CGRP.¹

3.3.2 *In Vivo* Non-Clinical Evaluations

Experiments in a hyperalgesic rat model have shown normalization of withdrawal latency of experimentally-induced ear pain with the administration of nasal CO₂. Subsequent experiments reported that this effect was decreased to a small extent if the duration of CO₂ administration was decreased by half the time, but there was a much more significant decrease in the anti-hyperalgesic effect if the flow rate was decreased by half.⁸

These experiments show that CO₂ had an anti-hyperalgesic effect in non-clinical models of pain, and that flow rate may be a significant determinant of the magnitude of this effect.

3.3.3 Clinical Evaluation in Healthy Volunteers

Study C011 was a randomized, double-blind, placebo-controlled study in healthy human volunteers designed to assess the tolerability of nasal CO₂ at different flow rates (0.22 L/min and 0.44 L/min) and using different nosepieces (direct versus indirect flow). Twenty-three subjects

were assigned to receive combinations of high or low flow rate (and placebo) with each type of nosepiece.

In C011, the most common AEs reported were related to the administration site (described in different terms such as nasal discomfort, tingling, burning, pain, stinging, irritation, etc.), lacrimation, rhinalgia, ear/nose/throat discomfort or pain, unusual/unpleasant taste, headache, and rhinorrhea. Additional AEs reported were dizziness/lightheadedness, post-nasal drip, nasal congestion, pressure at forehead or sinus, local hypothesia, left-side facial pain, numbness in throat, wheezy cough, and hot flashes. In general, subjects were able to tolerate the nasal CO₂ administrations, with approximately 90% of administrations being completed. The higher flow rate and direct flow nosepiece were not as well-tolerated as the lower flow rate and diffuse flow nosepieces.

3.3.4 Clinical Evaluations in Acute Migraine

To date, approximately 820 subjects with acute migraine have participated in clinical trials to evaluate the safety and preliminary efficacy of nasal CO₂ compared to a placebo control. Experience with nasal CO₂ to date support that nasal CO₂ can be administered safely at the doses planned for the current protocol. The data from these studies are summarized briefly below.

